## GLOSSARY OF ABBREVIATIONS

AE	Adverse event
BHA	Benign Histological Abnormalities
BMI	Body Mass Index
CAG	Confidentiality Advisory Group
CI	Chief Investigator
CRF	Clinical Research Fellow
fP-iGBC	Feasibility/Pilot phase of P-iGBC (qP-iGBC and pP-iGBC together)
GBC	Gallbladder Cancer
GBD	Gallbladder Dysplasia
GPo	Gallbladder Polyp(s)
HRA	Health Research Authority
ICF	Informed Consent Form
ICH	International Conference of Harmonisation
ICJME	International Committee of Medical Journal Editors
iGBC	Incidental Gallbladder Cancer
NHS	National Health Service
NRES	National Research Ethics Service
PES	Plain English Summary
PI	Principal Investigator
P-iGBC	Predicting Incidental Gallbladder Cancer (short title/ acronym for full study)
PIS	Participant/ Patient Information Sheet
PPIE	Patient and Public Involvement and Engagement
pP-iGBC	Pilot P-iGBC Component
qP-iGBC	Qualitative P-iGBC Component

Date and Version No: 04/11/2024; Version 1.3

R&D	NHS Trust R&D Department
REC	Research Ethics Committee
RHA	Routine Histological Analysis
SAE	Serious Adverse Event
SAP	Statistical Analysis Plan
SAR	Serious Adverse Reaction
SHA	Selective Histological Analysis
SOP	Standard Operating Procedure
TBC	To Be Confirmed
UHP	University Hospitals Plymouth NHS Trust
UK	United Kingdom
XC	Xanthogranulomatous Cholecystitis

Date and Version No: 04/11/2024; Version 1.3

## KEY WORDS

Incidental Gallbladder Cancer, Gallbladder Cancer, Cholecystectomy, Histology, Gallbladder, Selective Histological Analysis, Histopathology, Adaptive design

## STUDY SUMMARY

**Study Title** Identification of Predictive factors of Incidentally detected **Gallbladder Cancer** and prospective validation of a scoring system to allow selective histological analysis of the gallbladder (**P-iGBC**).

**Study Design** Prospective, Multi-centre, Observational & Modelling Study with an internal pilot and adaptive design.  
Parallel, embedded qualitative study

**Study Participants** Adults undergoing cholecystectomy during the trial period, Biliary pathway patients and professionals involved in their care.

**Eligibility Criteria** Inclusion Criteria:

All adult patients ( $\geq 18$  years of age) undergoing cholecystectomy (including subtotal and remnant cholecystectomy) for benign indications:

1. Symptomatic Gallstone Disease
2. Biliary dyskinesia

Exclusion Criteria:

1. Imaging suspicious for/confirming type III & IV Mirizzi syndrome.
2. Previous or current diagnosis of biliary tree malignancies
3. Pre-operative concern or suspicion of Gallbladder or biliary tree malignancy
4. Presence of gallbladder polyps  $\geq 5$ mm
5. Biliary tree abnormalities, including Primary Sclerosing Cholangitis and Choledochal Cysts
6. Patients undergoing cholecystectomy as a part of, or incidental to, another procedure.

Date and Version No: 04/11/2024; Version 1.3

Planned Sample Size 300-500 (internal pilot) up to 30,000 (TBC on the result of an internal pilot)

Follow-up Duration Ends on report of histopathology result. No longitudinal follow-up.

Planned Study Period June 2024-June 2029

[figure not shown]
Primary Objective Development and validation of a diagnostic score for incidental gallbladder cancer

Secondary Objectives Evaluation of willingness for and barriers to selective histological analysis of the gallbladder  
Incidence of incidental Gallbladder Cancer and associated benign abnormalities.  
Identification of the risk factors for incidental Gallbladder Cancer.

[figure not shown]
Date and Version No: 04/11/2024; Version 1.3

## STUDY FLOW CHARTS

### Quantitative component

### Qualitative component

Date and Version No: 04/11/2024; Version 1.3

## 1. INTRODUCTION

### 1.1 BACKGROUND

Incidental Gallbladder Cancer (iGBC) is a rare diagnosis following cholecystectomy, which is a common operation normally performed for symptomatic gallstone disease (1,2). Less common benign indications include gallbladder dyskinesia and gallbladder polyps. Overall, 67,819 cholecystectomies were performed in NHS England and Wales in the year to March 2022 and it is standard practice in the UK for cholecystectomy specimens to be sent for Routine Histological Analysis (RHA) to exclude underlying iGBC(1,3). The United Kingdom (UK) has a low incidence of iGBC of between 0.14-0.3%, which contrasts with high-incidence countries, for example in South America and South Asia, where it is as high as 1.18% (4–12). Other, non-cancerous abnormalities, termed Benign Histological Changes (BHC), such as Xanthogranulomatous Cholecystitis (XC) and Gallbladder Dysplasia (GBD), can be challenging to diagnose or differentiate from cancer macroscopically and therefore require histological examination. Combined, iGBC and BHC have an incidence in the UK of around 2% (4,6,13).

RHA is not unique to the UK, and is practised in most high-income countries, however it is expensive and requires examination of thousands of unremarkable gallbladders to diagnose relatively few patients with iGBC(1,8,10,14). We conservatively estimate that the cost of RHA in routine cholecystectomy is at least £5,055,228.26 annually, based on an historic estimate of the cost of processing individual specimens multiplied by the volume of cholecystectomies quoted above (1,8). In addition to the financial costs incurred by RHA, processing so many gallbladder specimens puts enormous pressure on histopathology services who are acknowledged to be overburdened and under resourced(15,16). This volume of specimens is particularly significant at present, as subsequent delays in processing NHS cancer specimens can anecdotally reach 4- 6 weeks, potentially delaying decisions on adjuvant treatment (e.g. chemotherapy) which, in some cases, may affect overall survival(17). As the incidence of iGBC is so low, it has been argued that sending every gallbladder specimen for RHA is unnecessary and could be replaced with Selective Histological Analysis (SHA), whereby gallbladders with no significant risk of iGBC or BHC would not be sent for histopathology(3,5,8–11,18–20).

Whilst SHA has the potential to significantly reduce costs and mitigate high pathological workloads, its safety is intrinsic to its success. Key to this is a good, clinically applicable method of risk-stratification, and current methods require improvement. Some centres in high-income countries already practice SHA, however the risk stratification methods and criteria by which gallbladders are selected for histopathology are not always clear (7,20). Proponents of SHA suggest that it is safe when specimen

Date and Version No: 04/11/2024; Version 1.3

selection is based on macroscopic inspection or uses a defined, algorithmic approach (5,9,11,14,21). However, review data suggests that macroscopic inspection misses between 23.1 and 33.3% of iGBC and that there are higher incidences of iGBC in RHA centres than in SHA centres. This implies that current selection methods lead to missed diagnoses(5,7,20). Although it is not clear why SHA has not been adopted in the UK, it has been suggested that UK surgeons are averse to taking responsibility for a missed diagnoses(21,22). Further, whether SHA is acceptable to patients in the UK is yet to be evaluated.

The risk factors for GBC are well recognised. Cholelithiasis is a pre-disposing factor, and there is a strong association with chronic cholecystitis, while acute cholecystitis confers a poorer prognosis (23–25). Other risk factors include age, ethnicity, female gender, jaundice, a raised alkaline phosphatase, certain intra-operative factors and findings (including macroscopic cholecystitis or a thick-walled gallbladder and a need for lengthy or open operations), a history of typhoid infection or pre-existing disorders of the biliary tree, such as Primary Sclerosing Cholangitis and Choledochal Cysts(7,10,13,14,19,26–28). Gallbladder polyps are also associated with GBC, with a well described relationship between the size of the polyp and likelihood of cancer. The risk is negligible in polyps under 5mm but rises above the 0.2% UK incidence of iGBC to a 1.2% risk of GBC when the polyp is between 5-10mm, and increases to 8.5% in polyps over 10mm(29). It is therefore recommended that patients with high-risk polyps over 5mm or any polyps over 10mm undergo prophylactic resection(30,31). In Mirizzi Syndrome, in which impacted stones fistulate into the Common Hepatic Duct, the risk of GBC and cholangiocarcinoma occur is even higher, occurring in up to 28% of patients(32–34).

Although these multiple risk factors for GBC are well recognised, there is no robust risk-stratification method which is suitable for use in routine cholecystectomy in the UK. If a clinically applicable diagnostic score was able to stratify patients by their risk of iGBC, it could facilitate SHA, but importantly may also enable early identification, intervention, or investigation in high risk patients. These two major benefits of a risk-stratification or diagnostic score have clear potential benefits for patients and the health service, so it is perhaps unsurprising that there are already two such diagnostic scores in existence. Both, however, are limited in their reliability by their methodology and in their generalisability to the UK because of the settings in which they were developed. The first study, from a Swedish group, developed a diagnostic score based on age, sex, presence of cholecystitis and jaundice(19). A Dutch group recently published a more methodologically sound, retrospective, multi-centre study (18). From a methodological viewpoint, the data from which both were derived were limited and poorly complete - the Dutch study was missing 30.9% of data - and

Date and Version No: 04/11/2024; Version 1.3

both resultant scores consequently failed to identify all patients with iGBC in validation. Furthermore, the studies relied on existing or prospectively collected registry variables and, as a result, neither captured or were able to utilise many of the multiple known pre- and intra-operative risk factors. Further, both studies were conducted in settings in which SHA is already sporadically practiced, which may have meant that iGBC diagnoses were missing from their datasets leading to skewed data.

When comparing the populations in question, a further problem with the use of these scores arises. Compared to other European countries where patients are often operated within days of presentation, NHS patients wait longer for their cholecystectomies and therefore risk recurrent inflammation (35–43). In this post-COVID-19 era, a higher proportion of UK cholecystectomies are being performed for inflammatory indications, and this may suggest that the UK prevalence of iGBC will increase or the prognosis be poorer(7,23,35). As a consequence, we are unable to generalise the findings of the Swedish and Dutch studies to our own population and there is, therefore, a need for a high quality and comprehensive diagnostic modelling study of UK patients, to accurately identify and stratify the risk of iGBC.

This study aims to collect the data required to develop a high-fidelity, clinically applicable diagnostic score with a high negative predictive value, and has the potential to facilitate SHA and early identification of patients at high-risk of iGBC in this country.

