## 1.2 RATIONALE FOR CURRENT STUDY

Stratifying patients undergoing routine cholecystectomy by their risk of iGBC could facilitate SHA, enabling significant financial savings and reduced histopathological workloads, and allow identification of the highest-risk patients, meaning that their care could be prioritised appropriately. Published diagnostic scores and historical techniques, such as macroscopic inspection, either fail to identify all cases of iGBC or are poorly generalisable to our population and, as such, are inadequate for use in the UK. Multiple risk and predictive factors are well established, but no dataset adequately encompasses them to develop and validate such a robust, UK-based diagnostic score for iGBC.

This study aims to build a dataset from which a validated diagnostic score could be developed.

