## 2. STUDY OBJECTIVES

### 2.1 PRIMARY OBJECTIVES

- To develop and validate a diagnostic score for iGBC in patients undergoing cholecystectomy for benign indications.

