## 4. STUDY DESIGN, PROCEDURES, AND INTERVENTIONS

### 4.1 STUDY DESIGN

Multi-centre, cross-sectional study for diagnostic modelling with an integrated internal pilot, an embedded, parallel, interview-based, qualitative study, and an adaptive design.

The internal pilot and parallel qualitative workstreams will form a feasibility phase of this study (fP-iGBC). Following this feasibility phase, data collection will pause for 18 to 24 months to allow time for analysis of the feasibility phase, additional funding to be secured, expansion of the study team and for centres to be recruited and registered.

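### Does naming a high negative predictive value as the goal of the score undermine the plan, when almost any method reaches one at 0.2% prevalence?

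*Protocol*

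**What the plan says.** The phrase at issue stands at the end of section 1.1, where the aim is a "clinically applicable diagnostic score with a high negative predictive value". It is one of several qualities named there. The same sentence also asks for high fidelity and for early recognition of high-risk patients, and the sentence before it asks for accurate identification and stratification of risk.

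The Background sets a safety standard for selective histology: "its safety is intrinsic to its success". It reports that "macroscopic inspection misses between 23.1 and 33.3% of iGBC", and says of the two published scores that "both resultant scores consequently failed to identify all patients with iGBC in validation". Section 1.2 sums up that existing methods "either fail to identify all cases of iGBC or are poorly generalisable to our population".

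The operative sections read differently. The primary objective in 2.1 is "To develop and validate a diagnostic score for iGBC in patients undergoing cholecystectomy for benign indications", with no performance measure attached. The outcome measures in 2.3 are rates, feasibility and validation. Section 6.1 sizes the study for model development. The progression table in 6.3 a uses completeness of variables and number of centres. Section 6.3 b lists discrimination, calibration and clinical usefulness, with net benefit as its example, in a list that is open. It also announces a detailed statistical analysis plan for each phase.

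**The concern.** The Protocol faults other methods for the share of cancers they miss, then names for its own score a measure that hardly reflects that share when the disease is rare. NPV depends on prevalence and specificity as well as on missed cases. At 0.2% prevalence every candidate, including doing no histology, scores close to 100%, and a score that misses more cancers can show the higher NPV.

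If acceptance of the score rested on NPV, an unsafe score could be declared safe. With 67,819 operations a year (section 1.1) and 0.2% prevalence there would be about 67,819 × 0.002 = 136 cancers. Missing 23.1 to 33.3% of them means about 31 to 45 a year, treating every operation as eligible.

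**Working it through.** **Inputs.** Prevalence p = 0.2%, Nagelkerke R² 0.3, 20 parameters and 20% incomplete data (section 6.1). UK incidence range 0.14 to 0.3% and missed share m = 23.1 to 33.3% for macroscopic inspection (section 1.1). Specificity is not given, so 30 to 90% is assumed.

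**Step 1: the plan's own figure.** The sample size is reproduced by the shrinkage criterion for a binary prediction model, with a shrinkage of 0.9 (assumed; the Protocol does not state it).

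- Maximum Cox-Snell R² = 1 − exp{2[p ln p + (1−p) ln(1−p)]} = 0.02844
- Anticipated R² = 0.3 × 0.02844 = 0.008533
- n = 20 / [(0.9 − 1) × ln(1 − 0.008533/0.9)] = 20,995.3, rounded up to 20,996
- 20,996 / 0.8 = 26,245

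Both match section 6.1. NPV enters nowhere, so the phrase in 1.1 has no bearing on the size of the study.

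**Step 2: NPV at 0.2% prevalence.** NPV = sp(1−p) / [sp(1−p) + m·p]. Sending no specimen (m = 1, sp = 1) gives 99.800%.

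| Missed share | sp 30% | sp 50% | sp 70% | sp 90% |
|---|---|---|---|---|
| 5% | 99.967% | 99.980% | 99.986% | 99.989% |
| 10% | 99.933% | 99.960% | 99.971% | 99.978% |
| 23.1% | 99.846% | 99.908% | 99.934% | 99.949% |
| 33.3% | 99.778% | 99.867% | 99.905% | 99.926% |

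The lowest entry belongs to a rule worse than chance (sensitivity 0.667 + specificity 0.30 = 0.967, below 1).

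**Step 3: can the ranking reverse?** Yes. Missing 10% at specificity 30% gives 99.933%, below the 99.949% from missing 23.1% at specificity 90%. The reversal persists at 0.14% incidence (99.953% against 99.964%) and at 0.3% (99.900% against 99.923%). It needs widely different specificities. Within each column of the table NPV falls as the missed share rises.

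**Step 4: is NPV empty of information?** No. Read as residual risk (1 − NPV) at specificity 70%, missing 23.1% leaves 0.066% and missing 5% leaves 0.014%, a ratio of about 4.6. The values look alike mainly because all are written as 99-point-something.

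**Step 5: would the planned measures catch the problem?** Net benefit = true positives/n − (false positives/n) × odds of the threshold risk. Each missed cancer lowers the first term directly. For the pair in step 3:

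- true positives per patient: 0.002 × 0.90 = 0.001800 against 0.002 × 0.769 = 0.001538, a difference of 0.000262
- false positives per patient: 0.998 × 0.70 = 0.6986 against 0.998 × 0.10 = 0.0998, a difference of 0.5988
- 0.5988 / 0.000262 ≈ 2,285 extra cancer-free specimens per extra cancer found

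Net benefit sets out the exchange that NPV hides. A score with no information would also show up at once in the discrimination measure.

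**Step 6: would a sensitivity precision statement belong in 6.1?** With no cancer missed, the exact 95% lower limit is 0.025^(1/n): 91.6% for 42 events (20,996 × 0.002), 92.6% for 48 (30,000 × 0.8 × 0.002) and 94.0% for 60 (30,000 × 0.002). These limits hold for a cut-off fixed in advance. Section 6.3 b develops the score and validates it by resampling the same data, so a cut-off could be placed at the lowest-scoring cancer and give zero misses by construction. Printed in 6.1, the limits would be too favourable.

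**The case for a change.** The best argument for a change is that section 1.1 states the aim in the study's own voice, that it is the only place where a predictive property is named, and that none of the measures listed in 6.3 b is, by name, the share of cancers missed at the working cut-off. Rewording would cost little and needs no extra data. There is time for it too, since after the feasibility phase "data collection will pause for 18 to 24 months" and the target is then recalculated.

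Part of this stands. NPV on its own would be a poor test of safety here, and naming sensitivity and the proportion of specimens spared beside it would make the aim read better.

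It falls short of a reason to change the plan. The Protocol does not say that NPV alone will decide anything. NPV is also a fair thing to want from a rule-out score, because it answers what a surgeon asks of a gallbladder that is not sent. Missed cases are only part of the criticism of the published scores: incomplete data, absent risk factors and a different population are argued at least as fully, and section 1.2 states the ground as an either/or. Finally, the list in 6.3 b is open, and cut-off-specific sensitivity with intervals and optimism correction is standard content for the announced analysis plan.

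**Conclusion.** The arithmetic behind the concern is right, but nothing in the plan rests on it. At 0.2% prevalence NPV runs from 99.78 to 99.95% for methods missing 23.1 to 33.3% of cancers, against 99.80% for sending nothing, so a high NPV is no evidence of safety by itself. These figures assume specificities of 30 to 90%, and the reversed ranking needs specificities far apart.

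NPV appears in one Background phrase and in no objective, outcome, sample-size calculation, progression rule or analysis. Following sections 6.1 and 6.3 as written gives no wrong estimate or decision, and the planned discrimination, calibration and net benefit would expose a poor score. An analyst writing the detailed plan for a rule-out score would report sensitivity and specimens spared as a matter of course. This is a loose choice of words in the introduction, and no change to the plan follows.

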## 1.2 RATIONALE FOR CURRENT STUDY

Stratifying patients undergoing routine cholecystectomy by their risk of iGBC could facilitate SHA, enabling significant financial savings and reduced histopathological workloads, and allow identification of the highest-risk patients, meaning that their care could be prioritised appropriately. Published diagnostic scores and historical techniques, such as macroscopic inspection, either fail to identify all cases of iGBC or are poorly generalisable to our population and, as such, are inadequate for use in the UK. Multiple risk and predictive factors are well established, but no dataset adequately encompasses them to develop and validate such a robust, UK-based diagnostic score for iGBC.

This study aims to build a dataset from which a validated diagnostic score could be developed.

## 1.3 PARTICIPANT AND PUBLIC INVOLVEMENT AND ENGAGEMENT

Fortunately, we have had the support of a patient representative (AB) who has critically reviewed the study design and documents, and has provided valuable feedback. A second patient representative

Date and Version No: 04/11/2024; Version 1.3

(HW) has assisted in developing Plain English Summaries (PES) for formal PPIE consultation and grant applications.

The overall hypotheses and aims of the study were discussed with the PENPeg PPIE group's "Ideas Cafe" in its early development stages. The group unanimously supported the project, with several members expressing surprise at the current practice of routine histological analysis in cholecystectomy.

A formal PPIE consultation has been undertaken, in which five patients agreed to participate. Patients were provided with pertinent study documents and a PES before one-to-one meetings were held. For full report on the PPIE consultation, including full methodology and detailed results, please see [appendix 12](#).

Overall, consultation participants were very supportive of the study, stating that they were, "so much in favour of what you're doing," and that the study would be, "helpful for patients and... the medical profession". Most commented that they were surprised that gallbladders were routinely sent for analysis, and that they had not considered that cancer may, "complicate," their procedure. There was a general consensus that non-consented data collection was both justified and acceptable, as it was felt that the research was, "for the greater good," and that attempting to consent all patients would be, "impractical if [the protocol adopted] too formalised a route... [it] would cost too much and take a huge amount of time".

Some further changes to the protocol were made following PPIE consultation. One participant commented that the original initialism, PIGBC, and the associated logo read to them as "pig" and had a negative association with obesity as their perceived cause of gallstone disease. They suggested that the revised acronym P-iGBC held a much weaker association, and subsequently approved this and a revised logo. The opinion was supported by subsequent consultees. The original arrangements for non-consented data collection and informing patients of the study have also been revised. Although there was unanimous support for non-consented data collection, consultees felt that the wording of the protocol needed to be changed to encourage active informing of patients by clinicians in participating units. Consultees understood that this was different from informed consent but were satisfied that clinicians would be encouraged to draw patients' attentions to public notices of the study during the process of normal consultation and consent. Other minor changes to study documents resulting from the PPIE consultation include revisions to the PIS for the qualitative study and re-wording of public facing documents to improve clarity.

Date and Version No: 04/11/2024; Version 1.3

Given that this project affects histopathological services in that hypothesised changes to histological analysis protocols may affect their workload, we have sought and have been granted the support of our local histopathology department.

